#### Isometric handgrip training intervention and control

Participants will train three days per week at home for 1 month using a reliable and validated digital handgrip dynamometer (DynX, MD System, Inc., Westerville, OH, USA)) in a seated position. The isometric handgrip training protocol will consist of four sets (2 for each hand) of two-min sustained contractions starting at 30% MVC interspersed by 1-min resting periods (a total of 12-min). All training sessions will be remotely supervised via Zoom or phone call by a research team member to ensure compliance with the exercise prescription. Before each training session, MVCs will be re-assessed over three repetitions, each separated by 30-s, to ensure an accurate exercise prescription (13). The highest value will be used to determine the target intensity of the session. In the control/washout conditions, participants will be instructed to maintain their normal daily routines.

#### Post-intervention visits – isometric handgrip exercise acute bout

All participants will return to laboratory to complete the same acute bout of isometric handgrip exercise detailed in the baseline visit after the isometric handgrip exercise training and respective control.

#### Study endpoints (clinical trials):

NA

#### Study main outcomes

The main outcomes of this study are brachial BP (i.e., SBP and DBP), cardiac autonomic function (i.e., RMSSD, HF, and cardiac baroreflex sensitivity), and vascular function (i.e., flow-mediated dilation (FMD), and central pulse wave velocity (cfPWV)).

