### Sample size

Based upon an effect size of 0.160 and a drop-out rate of 15%, a priori power analysis (G-Power Version 3.1.9.3) for mixed ANOVA suggested a total of 50 participants are required to detect SBP mean differences of at least 5 mmHg over time and groups ( $\alpha = 0.05$ ,  $1-\beta=0.80$ ). Despite this mean difference obtained from a study that characterized BP responses after acute isometric handgrip exercise (7), we also aim to examine the effects of training on acute blood pressure responses to isometric handgrip exercise. Thus, given these differences in study design, we additionally set the effect size considering the small, standardized effect sizes ( $\leq 0.20$ ) for exercise training sciences (31).

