### Statistical analysis

Linear mixed models will be used to examine the effects of acute isometric handgrip exercise and training on BP, cardiac autonomic, and vascular function outcomes over time (i.e., aim 1, 2, and 3). These will be fitted with restricted maximum likelihood and applying Satterthwaite's method for approximating degrees of freedom for the F test using R lmerTest package (32). Fixed effects will be set as time, sex, training condition, and the random intercept as each participant. All models' residuals will be checked for normality and homogeneity of

variances using both Shapiro-Wilk and Levene tests, respectively, and through QQ plot inspection using the R performance package (33). Natural logarithm (Ln) transformations will be applied to HRV outcomes, as these are generally not normally distributed, but both transformed and untransformed data will be presented. Linear mixed models will be run with and without possible outliers identified through box plots as observations lying outside the 1.5 interquartile range. Unbiased effect sizes - partial omega squares ( $\omega^2$ ) will be estimated for each fixed effect and interactions terms and interpreted accordingly to the rough benchmarks set by Cohen (34) [small ( $\omega^2 < 0.05$ ), medium ( $\omega^2 < 0.25$ ), and large ( $\omega^2 > 0.25$ ) effects sizes]. Post-hoc comparisons will be performed using the Bonferroni correction, in the presence of significant fixed effects and interactions. MVC, %fat and free fat mass, and physical activity outcomes will be added to all linear mixed models as covariates, whereas resting HR and SRauc will be added to FMD and HRV main outcomes, respectively. In addition, the repeated measures correlation coefficient will be used to test associations between isometric handgrip exercise-induced BP changes before and after the training intervention and of BP with cardiac autonomic and vascular function outcomes (35). Multiple imputation procedures using full information maximum likelihood will only be used in case of a significant amount of missing data on outcomes (>15%) and if missing completely at random, as linear mixed modeling provides robust estimates for small to medium amounts of missingness (36). All statistical analyses will be conducted using R software, version 4.2.3 (37) with a significant level ( $\alpha$ ) of 0.05.

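### Seven unranked main outcomes are each tested at 0.05 with no control across outcomes; SBP drives the sample size but is not named primary, and no decisive model term is stated

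*Combined protocol and SAP*

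**What the plan says.** **Outcomes.** The section Study main outcomes states "The main outcomes of this study are brachial BP (i.e., SBP and DBP), cardiac autonomic function" and continues with vascular function. Counting the items gives two blood pressure outcomes (SBP, DBP), three autonomic (RMSSD, HF, BRS) and two vascular (FMD, cfPWV). No order or primary label is given, and the section Study endpoints (clinical trials) is answered as not applicable.

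**Sizing.** The Sample size section "suggested a total of 50 participants are required to detect SBP mean differences of at least 5 mmHg over time and groups", with alpha 0.05 and power 0.80. It adds that "we also aim to examine the effects of training on acute blood pressure responses to isometric handgrip exercise". SBP is not called primary here or anywhere else.

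**Analysis.** The Statistical analysis section uses linear mixed models for the effects of acute exercise and "training on BP, cardiac autonomic, and vascular function outcomes over time (i.e., aim 1, 2, and 3"). On model terms it says "Fixed effects will be set as time, sex, training condition, and the random intercept as each participant". Effect sizes "will be estimated for each fixed effect and interactions terms and interpreted accordingly", but the interactions are not listed and none is singled out. On multiplicity: "Post-hoc comparisons will be performed using the Bonferroni correction, in the presence of significant fixed effects and interactions". The section ends "All statistical analyses will be conducted using R software, version 4.2.3 (37) with a significant level" of 0.05.

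**The concern.** The Bonferroni rule works inside one outcome, after one of its model terms has already reached 0.05. It does not limit how many outcomes get that first chance. With seven outcomes of equal standing, any single significant result can be presented as the finding of the trial, and the reader cannot tell afterwards which result was meant to decide the question.

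Using SBP for the sample size does not settle this, because sizing on a variable does not designate it. Nor would naming SBP alone. A model with time, sex and training condition contains several terms, and the Sample size section itself points to two different questions: differences over time and between groups, and the effect of training on the acute response.

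**Working it through.** **Inputs.** Seven outcomes (Study main outcomes). Two-sided level 0.05 for each (Statistical analysis). No adjustment across outcomes. The documents give no correlations between outcomes, so a common correlation r is assumed and varied. All results are for one model term with every null true.

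**The plan's own figure.** The total of 50 cannot be reproduced from what is stated. The Sample size section gives the effect size (0.160), dropout (15%), alpha and power, but not the number of readings, the correlation between readings or epsilon. No conclusion about 50 is drawn here.

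**Step 1: seven outcomes.**

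- Independent: 1 − 0.95^7 = 1 − 0.698 = 0.302.
- Equal correlation r: 1 − ∫ φ(z) [Φ((1.96 − √r·z)/√(1−r)) − Φ((−1.96 − √r·z)/√(1−r))]^7 dz, integrated numerically.
- Results: 0.271 (r = 0.3), 0.230 (r = 0.5), 0.178 (r = 0.7), 0.114 (r = 0.9).

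**Step 2: the three aims as separate families.** The aims are numbered but not set out. Suppose they match the three domains, with 2, 3 and 2 outcomes.

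- Two outcomes: 1 − 0.95^2 = 0.098 if independent; 0.095, 0.091 and 0.084 at r = 0.3, 0.5 and 0.7.
- Three outcomes: 1 − 0.95^3 = 0.143 if independent; 0.136, 0.125 and 0.109 at the same values.

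Within each aim the error is therefore about 8% to 14% for r up to 0.7.

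**Step 3: after the fix.** With SBP tested at 0.05 and Holm at 0.05 over the other six only if SBP is significant, error over all seven for that term is at most 0.05. With Holm run regardless, the bound is 0.05 + 0.05 = 0.10.

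**Step 4: cost to a secondary outcome.** A test with 80% power at two-sided 0.05 has a standardised effect of 1.960 + 0.842 = 2.802. The first Holm step uses 0.05/6 = 0.0083, with critical value 2.638. Power there is Φ(2.802 − 2.638) = 0.565 (unrounded inputs), about 56%.

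**Step 5: which SBP readings.** The Research protocol text schedules main outcomes at rest, during exercise and at 5, 10, 30 and 60 minutes, which is six. Table 1 lists no BP at 10 minutes, which leaves five. In the Blood pressure section the brachial cuff is used only before and after exercise; the during-exercise reading is covered by the finger device. The set of readings in a brachial SBP model is therefore not settled.

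**The case against.** The strongest reply is that this is a mechanistic physiology study in healthy adults. It has three domains under three aims, reports an effect size for every term, and treats trial endpoints as not applicable. On that view a single primary outcome is a convention the plan need not adopt, and SBP is in any case the evident lead outcome.

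Part of this stands. The aims are not set out in the document, so a ranking could exist in text that is not available. Correlation lowers the figure: SBP with DBP and RMSSD with HF are plausibly related, and at r = 0.9 it is 11%. Labelling outcomes exploratory, with claims limited to match, is an acceptable alternative to testing them formally. The term brachial BP already points to the cuff, so only the during-exercise reading is open.

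The rest does not remove the point. The plan keeps the exploratory label for the individual responder analysis, while the main analysis has a prespecified alpha, power and sample size. Separate aims still leave about 8% to 14% within each.

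Three stronger readings are tempting but unsupported:

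- A reader might infer that 30% is the trial's actual error rate. It holds only for independent outcomes with all nulls true.
- A reader might multiply seven outcomes by the seven terms of a full three-factor model and quote 1 − 0.95^49 = 0.92. The plan does not list its interactions, the tests share data, and the terms answer different questions.
- A reader might infer that 50 participants is too few, or that it is adequate. With the number of readings, the correlation and epsilon unstated, the documents support neither.

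**Conclusion.** The point holds and should be corrected. Each single test is valid at 5%. What is missing is control across seven equally ranked outcomes, a designated primary outcome and a named model term. For one term with all nulls true, the chance of at least one false positive ranges from 30% under independence down to 11% at a common correlation of 0.9. The correlations are assumptions, and the per-aim figures further assume that the aims match the three domains. The absence of any rule across outcomes does not depend on either assumption.

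**What to change.** 1. Name brachial SBP as the single primary outcome. State which readings enter the model, and how the during-exercise reading is handled given that the cuff covers only before and after exercise.
2. Prespecify one model term for SBP, tested at two-sided 0.05. The choice is the investigator's; the study title and the Sample size section point to a term involving training and time, with sex.
3. Make the other six outcomes secondary, with one analysed form of each and Holm across them for the same term. Test them only if SBP is significant if error over all seven is to stay at 5%. Otherwise label them exploratory and report them without confirmatory claims.
4. Restate the 80% power for the named SBP term, giving its actual number of readings, the assumed correlation and epsilon.

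**Cost.** Protocol and SAP wording only. Secondary outcomes face a stricter threshold (Step 4 of the working), and under gating they are descriptive if SBP is not significant. The restated power may not be 80%.

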### Study Population

#### Eligibility criteria

##### Inclusion criteria

Eligible participants for this study are 1) persons with normal BP as defined by the American Heart Association (<130/90 mmHg) and ages between 18-40 years; 2) those with BMI < 30 kg/m^2; 3) persons with no cardiovascular risk factors and no clinically diagnosed cardiovascular disease; 4) persons recreationally active ( $\leq 2$  days of structured physical activity); and 4) able to speak and comprehend English.

##### Exclusion criteria

Prospective participants will be excluded if they report 1) diagnosed cardiovascular (e.g., coronary artery disease, heart failure), musculoskeletal (i.e., osteoporosis and sarcopenia), and kidney disease; 2) taking antihypertensive or other vasoactive medications and cardioactive medication; 3) obesity (i.e., BMI > 30 kg/m^2); 4) hypertension (i.e.,  $\geq 130/90$  mmHg); 5) diabetes mellitus (i.e., fasting HbA1 > 6.5%); 6) depression and anxiety disorders; 6) long COVID; 7) being a smoker; 8) pregnancy or menstrual irregularities among females.

#### Excluded vulnerable populations

Pregnant females will be excluded due to pregnancy-induced changes in hormonal concentrations and cardiovascular regulatory mechanisms.

#### Study Duration

We foresee that this study will be completed in one year. The estimated duration of individual participation in this study is 2 months and each visit to the laboratory will take approximately 2h.

#### Number of Participants

We aim to sample 50 young healthy adults, 25 males, and 25 females.

#### Study Setting

All study measurements will be conducted in Integrative Physiology Human Laboratory (IHPL) at the University of Massachusetts Boston located at [name] in the Quinn Administration Building. The isometric handgrip training intervention will be conducted at the home of each participant enrolled in this study.

#### Prior approvals:

NA

#### External IRB/ethics review:

NA.

#### Local permissions/local context:

NA

#### Recruitment methods

Recruitment will be conducted at the University of Massachusetts Boston and in the greater metropolitan Boston area. We will ask to place recruitment flyers at the University of Massachusetts Boston and to use the email services. Word of mouth will also be used as a recruitment strategy. All communication, including electronic and social media, will only be used to spread information about the study. Persons interested in this study will initiate contact via our study phone call line or the Integrative Human Physiology Laboratory email for further study details and subsequent screening for eligibility. We will only contact potential subjects as a follow-up to those who initiate contact with study personnel first. Prospective participants will be screened over the phone using the Physical Activity Readiness Questionnaire for Everyone (PAR-Q Plus), the International Physical Activity Questionnaire (IPAQ), and a health history questionnaire along with age, sex, and menstrual cycle regularity. To minimize coercion and undue influence on participants verbal and non-verbal/behavioral expressions will be used to assess possible objections or resistance to taking part in the study. At any time during the study, participants can withdraw without any negative consequences.

## Procedures involved

### Study assessment procedures

#### Cardiovascular function

During the study visits, all non-invasive cardiovascular function measurements detailed below will be done in a quiet climate-controlled room (22-24° C) after a 15-min resting period, during, and after the fatiguing handgrip exercise with participants in a supine position. Participants will be tested in a fasted state (4h) and have refrained from exercise, caffeine/alcohol intake, and vitamins/supplements in the last 24h. Cardiovascular function testing in females will occur without controlling for the menstrual cycle (33,34), given that a growing body of literature supports little to no variation in BP, cardiac autonomic (i.e., BRS), and vascular function outcomes (i.e., brachial artery FMD and cfPWV) at rest and during acute exercise across the menstrual cycle or oral contraceptive pill cycle (25,27–32).

#### *Blood pressure*

Participants will be asked to wear a non-invasive inflating and deflating finger cuff during all study visits. This will allow beat-to-beat BP to be recorded using finger plethysmography (Finometer; Finapres Medical System, Amsterdam, The Netherlands) before, during, and after isometric handgrip exercise in the supine position. Beat-to-beat BP will be averaged offline over 2 to 5-min using Lab Chart 8 (ADIInstruments, BellaVista, NSW, Australia). Beat-to-beat dynamic fluctuations in BP induced by acute isometric handgrip exercise will be quantified through BP variability indices including spectral methods using the adapted HRV module of Lab Chart 8. This will give insight into sympathetic outflow to blood vessels (14,15).

**Brachial BP** of the right arm will also be measured three times at 1-minute intervals before and after isometric handgrip exercise using an automated blood pressure cuff (HEM-7311-ZSA; Omron Healthcare Co, Ltd, Kyoto, Japan) (16). Measurements will be accepted if they do not differ > 4 mmHg, and the average of the last two will be used for data analysis (16). Mean arterial pressure will be estimated as  $2/3 \text{ DBP} + 1/3 \text{ SBP}$ .

**Central BP** will be assessed via carotid artery tonometry (NIHem, Cardiovascular Engineering Inc., Norwood, MA). Brachial systolic and diastolic cuff BPs will be used to calibrate the peak and trough of the signal-averaged pressure waveforms. Carotid pressure waveforms will be calibrated with diastolic and integrated mean brachial cuff pressure. Central BP is then estimated from the calibrated carotid pressure. Central pulse pressure will be calculated as the difference between the peak and trough of the calibrated carotid pressure waveform.

**24-hour ambulatory BP** will be monitored with the AMBPro devices (SonmoMedics, Randersacker, Germany), which uses pulse transit time technology. The cuff will inflate every hour at night and every 30 min during the day, for measurement of standard brachial BP during the inflation/deflation cycle. BP between cuff inflation is determined continuously from pulse transit time measurements derived from concurrent electrocardiogram and photoplethysmography recordings. This device validated by the European Society of Hypertension can also be programmed to obtain pressures using conventional oscillometry during cuff inflation. Participants will be instrumented with four limb electrodes on their chest for the electrocardiogram recording. A cuff will be placed on their non-dominant arm that contains the photoplethysmography sensor. Data will be exported from the device for off-line analyses of the 24-hr BP and heart rate signal. The physical activity and movement sensors embedded within the device will allow for clear identification of daytime and nighttime pressures.

### *Cardiac autonomic function*

We will place electrodes directly on the skin of each participant to obtain the ECG trace required to estimate both heart-rate variability and baroreflex sensitivity outcomes.

**Heart rate variability and baroreflex sensitivity:** R-R intervals will be sampled at 1000 Hz frequency to obtain digital R waves digital sequences using the single ECG lead module of PowerLab data acquisition system (ADInstruments, BellaVista, NSW, Australia). All data acquisition and offline analyses will be conducted following the standards of the Task Force of the European Society of Cardiology and the North American Society of Pacing and Electrophysiology (17). Offline heart rate variability (HRV) analyses will be performed over a 2-min time series for each time-point (i.e., baseline, during and 5, 30 and 60 min after exercise) using the HRV analysis module of Lab Chart 8 (ADInstruments, BellaVista, NSW, Australia) (18). Main time-domain indices of interest include the standard deviation of NN intervals (SDNN) – a measure of overall variability, and the root mean square of the sum of the squares of the differences between NN intervals (RMSSD) – a measure of cardiovagal modulation. In addition, non-linear time-domain parameters will be derived from the Poincaré plot, including the vertical deviation that reflects mainly cardiovagal modulation (SD1), the longitudinal deviation (SD2), and the non-linear ratio SD1/SD2 an index of autonomic balance analogous to LF/HF ratio (19). The time-frequency domain analysis will be conducted using the Lomb-Scargle Periodogram, which permits accurate estimation of low (0.04 to 0.15 Hz) and high-power frequency (HF) power bands (0.15 to 0.40 Hz) in absolute and normalized power units during exercise conditions. Cardiac baroreflex sensitivity (BRS) will be estimated via the spontaneous sequence method over 2 min through the Lab Chart 8 baroreflex macro. Briefly, this method identifies ramps where increases in SBP ( $> 1$  mmHg) are coupled with increases of the RR interval ( $> 4$  ms) (linearly correlated) that occur over at least 3 beats (minimum sequence). The minimum acceptable correlation coefficient between SBP and RR interval ramps will be 0.80. Then, baroreflex sensitivity is estimated as the average of all regression slopes between the SBP and RR interval.

### *Vascular function*

During the vascular function measurements, we will ask participants to lie quietly in the supine position. They will also experience a forearm occlusion to permit the assessment of endothelial function.

**Endothelial function:** will be non-invasively assessed via brachial artery FMD, which represents nitric oxide-dependent vasodilation and closely correlates with the endothelial function of the coronary arteries (20,21). FMD will be assessed in the right brachial artery with an ultrasound (Arietta V750, Fujifilm, Tokyo, Japan) equipped with a 7.5-MHz linear array probe incorporating a 5-MHz Doppler transducer, placed  $\sim 4$  cm above the antecubital fossa, and held by a stereotactic clamp following standard guidelines (22,23). Reactive hyperemia will be induced by rapid cuff deflation following a forearm occlusion (Hokanson SC10, Bellevue, WA 98005, USA) maintained for 5-min at 250 mmHg. Changes in intraluminal brachial artery diameter will be tracked with automated edge-detection software (FMD studio, Quipu srl, Pisa, Italy) allowing precise measurement of the artery diameter (23). Doppler measurements of peak hyperemic blood velocity with an insonation angle of  $\leq 60^\circ$  will allow calculation of FMD main stimuli - shear rate as  $(4 \times \text{peak blood velocity} / D_{\text{baseline}})$  (23). All FMD analyses will be done offline using the FMD studio. FMD will be presented both as an absolute change ( $\text{FMD (mm)} = D_{\text{peak}} - D_{\text{baseline}}$ ) and as a relative change ( $\% \text{ FMD} = (D_{\text{peak}} - D_{\text{bas}}/D_{\text{baseline}}) \times 100$ ) in diameter. If a non-linear ratio between  $D_{\text{peak}}$  and  $D_{\text{bas}}$

is observed (B coefficients < 1), %FMD will be allometrically scaled for  $D_{baseline}$  (24,25). In addition, blood flow will be estimated as (Mean blood velocity) x (Brachial Cross-Sectional Area) x (60). Brachial artery blood flow will be measured in both exercising and non-exercising arms. All FMD scans will be conducted by the same researcher with inter-day measurements CV <15% (22,23).

**Arterial stiffness:** cfPWV the non-invasive gold standard measurement of central arterial stiffness will be assessed using an applanation tonometry automatic device (NIHem, Cardiovascular Engineering Inc) with participants lying supine. Briefly, common carotid artery and femoral artery pressure waveforms will be recorded using a high-fidelity strain-gauge transducer placed separately on both arteries permitting pulse transit time estimation through the ECG R-wave to the foot of the applanation waves (intersecting tangent foot-to-foot method). PWV is then calculated by dividing carotid-femoral distance (subtraction method) by pulse transit time (26). Pulse waveforms velocity from carotid-brachial and radial artery tracts will also be measured and interpreted as regional indices of upper limb stiffness. All measurements will be conducted by reliable operators (i.e., CVs < 5%) on the right side of the body and ensuring that repeated measurements differ by less than < 0.5 m.s (27). Brachial waveforms and BP will be used to calibrate central pressure waveforms.

Local carotid stiffness and blood flow will also be measured from the common carotid artery using a high-resolution ultrasound (Arietta 750, Fujifilm, Tokyo, Japan) and high frequency (7.5 MHz) linear probe. Carotid artery diameter and blood velocity will be measured using the wave intensity mode with the probe placed on the skin over the carotid artery approximately 1-2 cm to the proximal carotid bifurcation with a 60-degree insonation angle. Carotid stiffness indices such as  $\beta$  stiffness (eq.1) and PWV (eq.2) will be estimated according to the manufacturer's formulas:

$$(eq. 1) \beta = \ln \left[ \frac{SBP/DBP}{(D_{syst} - D_{diast})/D_{diast}} \right]$$

Where,  $\beta$  is beta stiffness; SBP, brachial systolic blood pressure, DBP, diastolic blood pressure;  $D_{syst}$ , brachial artery diameter during systole;  $D_{diast}$ , brachial artery diameter during diastole.

$$(eq. 2) PWV = \sqrt{((\beta \times DBP)/(2\rho))}$$

Where, PWV is brachial artery pulse wave velocity;  $\beta$ , beta stiffness, DBP, brachial diastolic blood pressure; and  $\rho$ , is blood density - assumed constant (1050 kg/m^3).

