## Study intervention

### Baseline visit – fatiguing bout of Isometric handgrip exercise

All participants will rest for 15-min, and then the MVC will be determined based on three attempts, each separated by 30-s, with participants in a supine position. The highest MVC will be used to define the exercise workload (30% MVC). Then, participants will perform a fatiguing bout of unilateral isometric handgrip exercise in the supine position using a digital handgrip transducer intertwined with a data acquisition system (Powerlab 16/35; ADInstruments, BellaVista, NSW, Australia). Participants will use their dominant hand and will hold the isometric contraction until task failure. The failure criteria will be defined as the inability to sustain the contraction force within 5% of the target MCV percentage (i.e., 30%). We chose to set the intensity at 30% MVC as this is the standard target intensity of isometric handgrip exercise protocols (7–9) and no differential BP responses have been reported when different intensities (i.e., 20 vs 30 and 45% MVC) are

used (10–12). Based on previous research, we expect that participants will fatigue within 3 to 5 min (i.e., time to task failure) (12). Participants will receive both visual and auditory feedback to maintain the target exercise intensity throughout the session. The same fatiguing bout protocol will be used before and after the training intervention.

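### FMD is always scanned in the right arm but the acute bout uses the dominant hand, so left-handers supply non-exercised-arm data that may dilute the acute FMD response

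*Combined protocol and SAP*

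**What the plan says.** The Baseline visit section has participants "perform a fatiguing bout of unilateral isometric handgrip exercise in the supine position" and specifies the side by dominance: "Participants will use their dominant hand and will hold the isometric contraction until task failure". The bout does not change between visits: "The same fatiguing bout protocol will be used before and after the training intervention".

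The Vascular function section fixes the side of the FMD scan anatomically: "FMD will be assessed in the right brachial artery with an ultrasound". Table 1 places FMD at rest and at 10, 30 and 60 minutes after the bout. The same section provides for both limbs, but only for another measure: "Brachial artery blood flow will be measured in both exercising and non-exercising arms".

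Home training is done with both hands: "four sets (2 for each hand) of two-min sustained contractions".

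FMD is listed under Study main outcomes. The inclusion and exclusion criteria do not mention handedness. The Statistical analysis section lists time, sex and training condition as fixed effects, a random intercept per participant, and a set of covariates. None of these refers to handedness or to the exercised limb.

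**The concern.** In a right-hander the scanned artery supplies the forearm that has just worked to task failure. In a left-hander it supplies the forearm that rested. The post-exercise FMD time course then averages a local-limb response with a remote-limb response, in proportions set by whoever happens to enrol. The random intercept absorbs a constant difference in level between people, but not a difference in the shape of the time course.

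What is exposed is the rest-to-post-exercise change in FMD and its interactions with sex and training. That change is one of the things the trial sets out to describe, and sex is the question in its title. The protocol does not appear to use right and dominant interchangeably: the ambulatory cuff is assigned to the non-dominant arm, so side is chosen by dominance where that is intended.

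**Working it through.** **The plan's own figure.** The point contests no stated number. The only sizing figure is 50 participants, based on SBP with effect size 0.160, α = 0.05, power 0.80 and 15% drop-out. The number of time points and the within-person correlation are not given. Taking 0.160 as Cohen's f, and assuming two sexes, six time points, correlation 0.5 and sphericity, the within-between interaction needs 44. Then 44/0.85 = 51.8, or 52, close to 50. The match depends on the assumptions: five time points give 48, and 48/0.85 = 56.5, or 57. Nothing in this sizing refers to FMD.

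**Inputs for the dilution.** Neither of these is in the documents, so both are assumed.
- p, the share of left-handers: 5%, 10%, 15%.
- r, the acute FMD response in the non-exercised arm divided by that in the exercised arm: 0, 0.5, 1.

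**How many participants.** The expected number of left-handers is 50p = 2.5, 5, 7.5. The chance of at least one is 1 − (1 − p)^50 = 92%, 99.5%, over 99.9%.

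**Share of the acute effect kept.** A fraction 1 − p contributes the full effect and a fraction p contributes r times it, so kept = 1 − p(1 − r). For example, p = 10% and r = 0.5 give 1 − 0.10 × 0.5 = 0.95.

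**Power, illustrative.** Take a two-sided contrast with nominal 80% power, so the expected z is 0.842 + 1.960 = 2.802. Power after dilution is Φ(2.802 × kept − 1.960), ignoring the far tail. For p = 10% and r = 0: 2.802 × 0.90 − 1.960 = 0.562, and Φ(0.562) = 71%.

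| p | kept, r = 0 | power | kept, r = 0.5 | power | kept, r = 1 | power |
|---|---|---|---|---|---|---|
| 5% | 95% | 76% | 97.5% | 78% | 100% | 80% |
| 10% | 90% | 71% | 95% | 76% | 100% | 80% |
| 15% | 85% | 66% | 92.5% | 74% | 100% | 80% |

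**Sex-by-time contrast.** If the acute effect is the same in both sexes, the spurious sex difference, as a share of that effect, is (difference in left-handers / 25) × (1 − r). A split of 1 of 25 against 4 of 25 gives 3/25 = 12% at r = 0, 6% at r = 0.5 and nothing at r = 1. With equal true rates in the two sexes, a gap of three or more arises by chance with probability about 10%, 23% and 32% at p = 5%, 10% and 15% (two independent binomials of 25).

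**What is not touched.**
- cfPWV is measured between carotid and femoral arteries and is not tied to the exercised forearm.
- Brachial blood flow is planned in both arms.
- Resting FMD before and after training compares the same arm within each person, and that arm is trained whichever hand is dominant.

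**The case against.** The strongest reply is that a fixed scanning side is a reasonable choice. The protocol presents FMD partly as a marker of coronary endothelial function, not only as a local forearm measure. Cuff BP and tonometry are also right-sided (for cuff BP: "of the right arm will also be measured three times at 1-minute intervals before and after isometric handgrip exercise"). Scanning a few left arms exchanges one source of heterogeneity for another. This stands as far as the choice of arm is concerned: the documents do not say which limb response the acute FMD series is meant to represent. It does not remove the mismatch, because under the current text the series represents one limb in most participants and the other limb in the rest. The right-sided cuff readings are mentioned only as context; nothing here implies that they are affected.

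Three stronger readings are tempting, and the documents do not support them.
- *Left-handers do dilute the acute vascular effect.* This needs a smaller FMD response in the non-exercised arm, and the documents give no figure for that. Setting r = 0 gives the largest loss for r between 0 and 1; it is not a central estimate. The claim also cannot extend to all vascular outcomes, since only post-exercise FMD is exposed.
- *The trial loses power from 80% to about 71%.* No power is claimed for FMD, so there is no 80% to lose. The power column shows scale only.
- *The sex or training comparison is confounded by limb.* A sex shift needs both an uneven split of left-handers and a limb difference, and no handedness figures by sex are given. For training, each participant keeps the same limb mapping at every visit and trains both hands, so the risk to the training-by-time contrast is some dilution, not confounding.

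**Conclusion.** The inconsistency is real and no other passage resolves it: in left-handers, post-exercise FMD is taken from the arm that did not exercise and is pooled with exercised-arm data. The consequence is possible and modest, not demonstrated. With 5–15% left-handers, the acute FMD effect is reduced by 5–15% at r = 0, by 2.5–7.5% at r = 0.5, and not at all at r = 1. An illustrative contrast with 80% power would fall to 66–76% or 74–78%, or stay at 80%. These ranges rest on assumed values of p and r and on a normal approximation. This is a worthwhile, inexpensive improvement to one main outcome, not a threat to the trial as a whole.

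**What to change.** In the Endothelial function paragraph, specify that FMD is scanned in the exercised (dominant) arm in every participant. This changes one line, makes the acute FMD series describe a single limb response, and costs left-arm probe set-up in a few participants.

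If the right arm is kept, state that choice, record for each participant which arm exercised, and report a sensitivity analysis of the acute FMD models excluding anyone whose scanned arm was not the exercised arm. This costs one recorded variable and one additional model run. An indicator for scanned arm equal to exercised arm, with its interaction with time, is optional; with about five left-handers expected at p = 10%, it would be estimated imprecisely and should not replace the sensitivity analysis.
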